Appendix E: Study Product Preparation Protocol

SOP/ Step #	STAT: A Phase 2b, Randomized, Double-blind, Placebo-controlled, Multi-center Clinical Trial of Allogeneic Bone Marrow-Derived Human Mesenchymal Stromal Cells for the Treatment of Acute Respiratory Distress Syndrome	Tech Initials												
G.5	UCSF Parnassus Heights Patients ONLY: Deliver cells to bedside nurse or doctor.	 N/A												
G.6	Document product issue using FORMS-0124 "Issue Log". Time Released to Courier: _____  N/A if transported by BMT Lab													
DO NOT TAKE THIS PSS TO ICU														
Section H: Quality Control (QC) Testing														
H.1	Use QC sample (from step D.7 or D.8) to inoculate sterility cultures.  Use technique described in SOP-0912 "Sterility Testing for Cellular Therapy Products and management of Positive Cultures".  Label bottles with: DIN, Date, hMSC Clinical Trial and Tech's initials. Aerobic & Anaerobic sterility testing Sent on: _____ by: _____													
H.2	Sterility Results:  Positive Notified to: _____ Date/Time: _____  Negative	Sterility Result review by/date: _____												
H.3	Using QC sample (from step D.8) perform:  WBC count via hemocytometer  Trypan Blue Viability Testing: Refer to SOP-0935 "Trypan Blue Viability Procedure"  Time Viability was Done: _____  Calculations using memacytometer: 
  
 	Viable Cell Count	Total Cell Count (Viable + Non-Viable)	
   
 Side 1			
 
 Side 2			
 
 TOTAL COUNT	(H)	(I)	
  
 $\frac{(\text{H})}{(\text{I})} \div \frac{(\text{I})}{(\text{I})} \times 100 = \frac{(\text{H})}{(\text{I})} \% \text{ Cell Viability (J)}$ 
If % Cell Viability is <70 notify [contact] and [contact] within 24 hours.
		Viable Cell Count	Total Cell Count (Viable + Non-Viable)	Side 1			Side 2			TOTAL COUNT	(H)	(I)	Calculated by/Date: _____ Verified by/Date: _____
		Viable Cell Count	Total Cell Count (Viable + Non-Viable)											
Side 1														
Side 2														
TOTAL COUNT	(H)	(I)												
		 N/A PLACEBO												

Appendix E: Study Product Preparation Protocol

SOP/ Step #	STAT: A Phase 2b, Randomized, Double-blind, Placebo-controlled, Multi-center Clinical Trial of Allogeneic Bone Marrow-Derived Human Mesenchymal Stromal Cells for the Treatment of Acute Respiratory Distress Syndrome	Tech Initials																																
H.4	
Calculate TNC count and recovery %:
 
  
 TABLE 4	
 
 QC SAMPLE: Total Cell Count Thawed/Recovered	
 
 Patient Name:	Study ID:	DIN:	Product Code(s)	
   
 Total Cell Count (Viable + Non-Viable)	(I)	
 
 Total Cells/mL = $(10^6) = (I) \div (\# \text{ of large squares counted}) * 2$ (TB Dilution factor) * (any other dilution) * 1×10^4	(K)	
 
 Total Cells thawed/recovered = $(x 10^8) = (K) * 300 \text{ mL}$	(L)	
 
 Total Viable Cells = $(10^8) = (L) * (J)$	(M)	
 
 Viable Cells Recovery (%) = $(M) / (A) \times 100$		
  
 
If % Viable Cells Recovery is <70 notify [contact] and [contact] within 24 hours.
	TABLE 4				QC SAMPLE: Total Cell Count Thawed/Recovered				Patient Name:	Study ID:	DIN:	Product Code(s)	Total Cell Count (Viable + Non-Viable)			(I)	Total Cells/mL = $(10^6) = (I) \div (\# \text{ of large squares counted}) * 2$ (TB Dilution factor) * (any other dilution) * 1×10^4			(K)	Total Cells thawed/recovered = $(x 10^8) = (K) * 300 \text{ mL}$			(L)	Total Viable Cells = $(10^8) = (L) * (J)$			(M)	Viable Cells Recovery (%) = $(M) / (A) \times 100$				
Calculated by/Date: Calculated by/Date:
 
Verified by/Date: Verified by/Date:
 
 N/A PLACEBO  N/A PLACEBO

TABLE 4																																		
QC SAMPLE: Total Cell Count Thawed/Recovered																																		
Patient Name:	Study ID:	DIN:	Product Code(s)																															
Total Cell Count (Viable + Non-Viable)			(I)																															
Total Cells/mL = $(10^6) = (I) \div (\# \text{ of large squares counted}) * 2$ (TB Dilution factor) * (any other dilution) * 1×10^4			(K)																															
Total Cells thawed/recovered = $(x 10^8) = (K) * 300 \text{ mL}$			(L)																															
Total Viable Cells = $(10^8) = (L) * (J)$			(M)																															
Viable Cells Recovery (%) = $(M) / (A) \times 100$																																		
Section I: Clerical Documentation																																		
I.1	
The remaining volume from the QC sample will be given to the clinical research team for testing. Contact [name] by text [contact] and email [contact] to schedule a pickup.
 
 Place a syringe tip cap on the syringe and store at 2-8°C.  Make a copy of TABLE 4 and send with QC sample.
																																	
I.2	
Order IECTW to the ZZ account using Sunquest: Accession # _____
																																	
I.3	
Infuse cells in the BMT Inventory Database
 
  Using the Tank Summary screen, select a bag that was thawed by its location in the database.  Then select Discard/Transfuse Collection from the drop down  Select "discard"  In the Disposition box, enter the patients Name and MRN  Select the check boxes that correlate with the bags that were infused to the patient  Submit Edits  Print the screen and file in the patients records 	
 N/A PLACEBO
																																

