Appendix E: Study Product Preparation Protocol

SOP/ Step #	STAT: A Phase 2b, Randomized, Double-blind, Placebo-controlled, Multi-center Clinical Trial of Allogeneic Bone Marrow-Derived Human Mesenchymal Stromal Cells for the Treatment of Acute Respiratory Distress Syndrome	Tech Initials /Date
Section A: hMSC Product Receipt		
A.1	When receiving hMSC products, follow Instruction located on the hMSC Receipt Instructions document located in the Tree. HPCT Adult Lab >>Immuno>>hMSC ARDS Trauma >>Current Forms >>hMSC Receipt Instructions	
Attention Lab Staff: Keep doctors, nurses, and research personnel blind at all times.		
Section B: Preparation and Randomization on the Day of Infusion		
B.1	Assign a UCSF DIN.  Call PIC to assign a DIN number on the Apheresis Collection Number Accountability Log  Place the sticker on page one of this PSS.	
B.2	Fax order received: ARDS MSC STUDY ORDERS: Preparation and Randomization for cell infusion. This order will include all the information needed in the Randomization Portal (A second order must be received before thawing cells) Note: There is a time window of about 45 minutes until the next order is faxed.	
B.3	
Randomization Procedure:
 
 1. To access the electronic randomization system, go to www.studydata.net. 2. Login and select "statrand" from the dropdown box. 3. From the Main Menu dropdown select "New Randomization". 4. To randomize, enter all the data in the green section and press the Save button. 5. Note the Randomization time below. 6. Print a copy of the randomization page. 7. After you have pressed Save, exit this page by returning to the Randomization List form the Main Menu 
Randomized to:  INTERVENTION (CELLS)  CONTROL (PLACEBO)
 
Randomization Date/Time: _____
 
If patient is randomized to cell dose proceed to step B.4.
 
If patient is randomized to Placebo proceed to B.7
	
B.4	Prepare water bath and biosafety hood for thawing and reconstitution of product. Refer to: SOP-0906 Cellular Therapy Thawing Procedure SOP-0959 Laminar Flow Hood Operation and Maintenance Procedure	 N/A PLACEBO

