Appendix E: Study Product Preparation Protocol

SOP/ Step #	STAT: A Phase 2b, Randomized, Double-blind, Placebo-controlled, Multi-center Clinical Trial of Allogeneic Bone Marrow-Derived Human Mesenchymal Stromal Cells for the Treatment of Acute Respiratory Distress Syndrome	Tech Initials /Date
D.5	Mix gently and allow the cells to equilibrate for 5 minutes. Time End of Equilibration: _____	 N/A PLACEBO
D.6	While cells are in equilibration weigh the product bag to determine the final product volume. $\frac{\text{Weight of product bag (g)}}{\text{Weight of transfer pack (g)}} = \frac{\text{g}}{\text{mL}}$ <small>*Note: g = mL</small> Calculate the volume of reconstitution media needed to achieve a final volume of 300mL. $300\text{mL} - \frac{\text{Final Product volume (Q)}}{\text{mL}} = \frac{\text{mL}}{\text{Reconstitution Media to add (D)}}$	 N/A PLACEBO
D.7	Cell product - After equilibration, bring volume up to 300mL. 
  Add reconstitution media volume (D) to the "Infusion Bag" via needle free spike. Mix gently.  Mix gently.  This is the Final Investigational Product Bag. 
Placebo:
 
  300mL of reconstitution media is the Final Investigational Product Bag  Remove 20mL of reconstitution media for QC testing 
  Use a sterile syringe and syringe tip cap  Label with Study ID and "QC sample"  Re-label transfer pack as "Infusion Bag"  Go to step E.1 	

SOP/ Step #	STAT: A Phase 2b, Randomized, Double-blind, Placebo-controlled, Multi-center Clinical Trial of Allogeneic Bone Marrow-Derived Human Mesenchymal Stromal Cells for the Treatment of Acute Respiratory Distress Syndrome	Tech Initials /Date																

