12.3 Blinding

The study is designed as double-blinded. BMT laboratory staff will conduct randomization and prepare the study product. The BMT team will not share the randomization assignment to the participants and their families, as well as the research team (Site Investigators, Study Coordinators, Data Manager and Statistician). The data analysis conducted by the Statistician for the interim DSMB report after 60 patients, as well as the primary analysis of the main results will be undertaken in a blinded manner. The study treatment will be coded as "A" and "B".

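### As written, step I.1 of the UCSF product-preparation SOP sends patient-named, arm-revealing cell-count data to the clinical research team, against the SOP's own blinding rule and possibly against SAP 12.3 and 12.5

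*Protocol*

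**What the plan says.** Protocol Appendix E, step I.1, states: "The remaining volume from the QC sample will be given to the clinical research team for testing". It continues: "Make a copy of TABLE 4 and send with QC sample". The visible text of the step carries no placebo exemption box, so it applies to both arms.

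Table 4 (step H.4) is titled "QC SAMPLE: Total Cell Count Thawed/Recovered". It has fields for patient name, Study ID, DIN and product code, then total cells, viable cells and percentage recovery. Steps H.3 and H.4, which generate these figures, are marked not applicable for placebo.

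Three statements on blinding bear on this:

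- The same SOP, at the head of Section B: "Attention Lab Staff: Keep doctors, nurses, and research personnel blind at all times".
- SAP 12.3: "The BMT team will not share the randomization assignment to the participants and their families, as well as the research team". It lists that team as site investigators, study coordinators, data manager and statistician. SAP 12.5 keeps the same roles blind until data lock.
- Protocol 8.11 names the transplant-laboratory staff who prepare the infusion as not blinded. Apart from the DSMB, which reviews safety data unblinded (Protocol 12.6.1), no other unblinded role is described.

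**The concern.** The trial protects the blind carefully elsewhere. Bags and tubing are covered, placebo products receive a dummy expiry time, and Appendix E forbids taking the preparation worksheet to the ICU. Step I.1 then copies one arm-revealing table out of that worksheet, with the patient's name on it, and addresses it to a group whose title closely matches the one the SAP says must stay blind.

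The stake is mainly safety assessment. Under Protocol 6.2.2 and 12.2, the investigator decides whether an event is expected in ARDS, related to the product, and therefore reportable. An assessor who knows the arm may attribute the same event differently. There is also an indirect route to the primary endpoint: the oxygenation index depends on ventilator settings, and Appendix D imposes no fixed PEEP-to-FiO2 pairing.

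**Working it through.** No figure in the plan is at issue, so the check is a trace of the SOP by arm.

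| Step | hMSC | Placebo |
|---|---|---|
| QC sample drawn | D.8: cell suspension, volume = 300 mL minus the volume to infuse, at least 8 mL | D.7: fixed 20 mL of cell-free medium, labelled with Study ID |
| H.1 sterility culture | done | done |
| H.3 count and viability | done | not applicable |
| H.4 Table 4 | completed | not applicable |
| I.1 transfer to research team | sample plus completed Table 4 | sample with blank, not-applicable or absent Table 4 |

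1. **The form reveals the arm.** H.3 opens "Using QC sample (from step D.8) perform", and D.8 is the cell-product step. The placebo instruction at D.7 is "Remove 20mL of reconstitution media for QC testing", with no count to follow. Completed Table 4 means hMSC; otherwise placebo. With name and Study ID in the header, the arm is tied to a person.

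2. **The sample reveals it too.** One arm yields cells in a calculated volume, the other plain medium in a fixed volume. Withholding Table 4 alone would not close the gap.

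3. **The alerts carry the same information.** Viability or viable recovery below 70% triggers notice within 24 hours to contacts whose names are removed. Only an hMSC product can trigger either notice.

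4. **Timing.** Step D.2 puts viability testing 30 minutes to 1 hour after thaw starts. If the 24-hour clock runs from that result (an assumption; the SOP does not say), a viability notice arrives by 1 + 24 = 25 hours after thaw start. The primary-endpoint window ends 36 hours after infusion start, and infusion follows thaw. Such a notice can therefore arrive inside the window. Step I.1 sets no hold on release until data lock.

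5. **Comparison with the blinding rules.** The SOP banner covers research personnel without listing roles, so sending the form to any of them contradicts it. SAP 12.3 lists roles, so a breach of the SAP depends on which role the recipient holds.

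6. **Scope.** Appendix E says each facility writes its own SOP and receives UCSF's as an aid. Delivery steps G.4 and G.5 name two of the seven hospitals. Per-site enrolment is not given.

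**The case against.** The strongest reply is that the recipient is unknown. The pickup contact is removed from the public text and could be a laboratory scientist outside the four roles in SAP 12.3. Sending the form to such a person would not breach the SAP. That stands, and it limits the SAP part of the point to a conditional. It does not remove the conflict with the SOP's own banner, and no section supplied creates an unblinded role within the research team.

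A reader might infer that all 120 assignments are exposed. The documents do not support this. The SOP is one institution's, and nothing shows that other sites adopted step I.1; 120 is only a theoretical ceiling.

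A reader might also infer that ventilator weaning is biased because the research team controls it. Appendix D gives the decision to stop ventilation to the clinical team and bars weaning assessment in the first 24 hours after enrolment. Any effect on the oxygenation index through this route is indirect.

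Finally, Table 4 is not a form that exists for one arm only. It is printed in the common worksheet and completed for one arm. The inference about treatment is unchanged.

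**Conclusion.** The point holds as a defect in the written procedure. Followed literally, step I.1 discloses the arm of each named patient in both groups to the clinical research team, contrary to the SOP's blinding instruction. It would breach SAP 12.3 and 12.5 if the recipient holds one of the listed blinded roles. The documents do not show that anyone was in fact unblinded, and that should not be inferred.

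The size cannot be stated as a number: it is the patients treated at sites that use this step, a count the documents do not give. The most direct consequence would be for adverse-event relatedness and expectedness, and only where the recipient makes or influences those judgements.

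**What to change.** Amend step I.1 and the related notices as follows:

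- Release the QC sample and Table 4 only to a designated unblinded laboratory recipient with no part in enrolment, care, outcome assessment or adverse-event assessment.
- Remove the patient name and use a code whose link to the patient is held only by unblinded laboratory staff. The DIN will not serve: step G.2 puts it beside recipient name and Study ID on the infusion form, and Appendix H has a product identification number checked at the bedside.
- Send the below-70% viability and recovery notices to the same recipient.
- Withhold all these data from the SAP 12.3 blinded roles until data lock, then link them for the viability analysis in SAP 12.8.
- Confirm that the other sites' SOPs follow the same rule.

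The cost is SOP wording, a changed form header, a code list kept in the laboratory and a check of the site SOPs. No assay, sample-size or analysis change is needed, and the viability data remain available for the final report.

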Appendix F: Symptom Management During Infusion Guidelines

Appendix F: Guidelines for Symptom Management During Study Product Infusion

Adverse Reactions	Signs and Symptoms	Management
Hypersensitivity Hypersensitivity to allogeneic plasma proteins.	
• Dyspnea• Hypotension• Fever• Urticaria• Tachycardia• Hypoxemia	
• Pause MSC infusion• Check vital signs and O2 saturation• Hydrocortisone 1mg/kg IV• If still symptomatic after hydrocortisone, then diphenhydramine 25-50 mg IV• Increase supplemental O2 if O2 saturation is <93% and/or dyspnea• Resume MSC infusion after reasonable resolution of signs and symptoms.
Leukoagglutination Because some leukocytes may be present in the MSC preparation (although MSC purity will typically be >95%), leukoagglutination symptoms may occur.	
• Cough• “Tickle in throat”• Dyspnea• Hypoxemia• Chest pressure	
• Pause MSC infusion.• Check vital signs and O2 saturation• Increase supplemental O2 if O2 saturation is <93% and/or dyspnea.• Resume MSC infusion after reasonable resolution of signs and symptoms.
Volume Overload The volume of the MSC will be set at 300 ml total. Pulmonary edema may occur in this population. This can occur with or without concurrent cardiac dysfunction.	
• Dyspnea• Hypoxemia• Frothy, clear or pink sputum• Tachycardia• Lack of fever• Distended neck veins	
• Pause MSC infusion.• Check vital signs and O2 saturation.• Increase supplemental O2 if O2 saturation is <93% and/or patient is dyspneic.• Furosemide (≥ 10 mg IV)• Resume MSC infusion after reasonable reduction of signs and symptoms.
Transfusion Incompatibility The infusion of allogeneic MSC can be incompatible based on the presence of allo-antibodies in the donor and/or recipient serum. Transfusion incompatibility	
• Fever• Hypotension• Dyspnea• Low back pain• Dark urine• Drop in blood hemoglobin	
• Stop MSC infusion.• Check vital signs and O2 saturation.• IV fluid resuscitation immediately if hypotensive.• Forced diuresis and urinary alkalinization with IV D5W + 2 amps/l sodium bicarbonate.

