3.7.2.3 Risks of Transfusion Reaction

Known potential side effects of blood product transfusion include transient fever or chills. As per established regulatory requirements, bone marrow donors are prescreened for infection, reducing the risk of infection with HIV or hepatitis B or C from the hMSC cell product. Patients may experience more severe or life-threatening transfusion reactions, but these are exceedingly rare. Patients will be monitored during the infusion for signs of a transfusion reaction (urticaria or rash, bronchospasm) and medications will be readily available to treat a life-threatening transfusion reaction, should such a reaction occur.

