6.2.2 Safety Secondary Endpoints

Because the infusion of hMSCs could theoretically, as described above, cause transient occlusion of the pulmonary microcirculation which could be associated with a fall in systemic blood pressure, rising vasopressor dose, a rise in heart rate, an increase in arterial carbon dioxide concentration, or a fall in oxygenation, patients will be monitored closely during the study infusion for changes in these parameters. These events will be considered pre-specified infusion associated events if they occur within 6 hours of the initiation of study product infusion.

Pre-specified infusion associated events will be defined as:

(a) Within 6 hours of the initiation of study product infusion:

1. An increase in vasopressor dose greater than or equal to the following:
 - Norepinephrine: 10 mcg/min
 - Phenylephrine: 100 mcg/min
 - Dopamine: 10 mcg/kg/min
 - Epinephrine: 0.1 mcg/kg/min
 - Addition of a third vasopressor
2. New ventricular tachycardia, ventricular fibrillation or asystole
3. New cardiac arrhythmia requiring cardioversion
4. Hypoxemia requiring an increase in FiO₂ of 0.2 or more and an increase in PEEP of 5 cmH₂O or more to maintain SpO₂ in the target range of 88-95% that is not related to respiratory care/suctioning or ventilator dyssynchrony and persists for more than 30 minutes
5. Clinical scenario consistent with transfusion incompatibility or transfusion-related infection (e.g. urticaria, rash, new bronchospasm)

(b) Within 24 hours of the study product infusion:

1. Any cardiac arrest or death

We will also systematically collect and review the incidence and nature of serious adverse events that are different from what is expected in the clinical course of a critically ill patient with ARDS for the duration of the clinical trial (through day 28 from study product administration).

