F. During infusion of study product, patients will have continuous monitoring of arterial blood pressure, heart rate, rhythm, and oxygen saturation. Study personnel will be available for the duration of the infusion to monitor the patient. Body temperature will be monitored at a minimum at the start, midway through, and at the end of the infusion. Patients will be monitored closely for other signs of transfusion reaction, e.g., rash, urticaria or wheezing. If there are any signs of a transfusion reaction, the infusion of study product will be stopped immediately. Similarly, if a patient has a pre-specified infusion associated event, the infusion will be stopped. The infusion can also be stopped at the discretion of the study investigator if there is any concern about the patient's status.

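### Protocol 9.4 F and SAP Section 5 stop the infusion for urticaria; the Appendix F Hypersensitivity row says pause, treat and resume without naming who decides, and no text says which governs

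*Protocol*

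**What the plan says.** **The stop rule.** Protocol 9.4 F has patients watched for "other signs of transfusion reaction, e.g., rash, urticaria or wheezing" and continues: "If there are any signs of a transfusion reaction, the infusion of study product will be stopped immediately". It adds: "Similarly, if a patient has a pre-specified infusion associated event, the infusion will be stopped". The study investigator may also stop the infusion at discretion. SAP Section 5 repeats this text. Neither document mentions restart at this point. Protocol 3.7.2.3 also treats urticaria, rash and bronchospasm as signs of a transfusion reaction.

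**The pre-specified events.** Protocol 6.2.2 item 5 covers a clinical picture of transfusion incompatibility or transfusion-related infection, with urticaria, rash and new bronchospasm as examples. Item 4 covers hypoxemia needing both an FiO2 rise of at least 0.2 and a PEEP rise of at least 5 cmH2O, that is "not related to respiratory care/suctioning or ventilator dyssynchrony and persists for more than 30 minutes".

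**The bedside guidance.** Appendix H 3.13 and 4.11 refer staff to Appendix F. Its Hypersensitivity row, which lists urticaria and hypoxemia, says to pause, treat, and "Resume MSC infusion after reasonable resolution of signs and symptoms". The Leukoagglutination row ends the same way. The Volume Overload row ends "Resume MSC infusion after reasonable reduction of signs and symptoms". The Transfusion Incompatibility row begins with a stop and leaves the choice between restarting and aborting to the attending BMT physician. Appendix H 4.11 asks staff only to consider a pause or a stop when side effects are significant.

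**The concern.** Urticaria during the infusion falls under two written instructions. One orders a stop and is silent on what follows. The other orders a pause, treatment and resumption. Appendix F uses pause and stop as different actions, so the two words cannot simply be read as synonyms.

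At stake is whether a critically ill patient who has shown a sign that the protocol itself treats as a transfusion reaction is given the rest of an allogeneic cell product, and who takes that decision. Sites could answer differently while each follows a written text.

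**Working it through.** The plan states no figure on this point, so the check is a comparison of texts.

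**Step 1. The six rows of Appendix F.**

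| Row | Urticaria listed | Hypoxemia listed | First action | Restart |
|---|---|---|---|---|
| Hypersensitivity | yes | yes | pause | resume; no one named |
| Leukoagglutination | no | yes | pause | resume; no one named |
| Volume Overload | no | yes | pause | resume; no one named |
| Transfusion Incompatibility | no | no | stop | attending BMT physician decides |
| Cryopreservatives | no | no | pause | resume or give remainder; no one named |
| Infection/Endotoxemia | no | yes | stop | not mentioned |

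Urticaria is in 1 of 6 rows, and that row begins with a pause. Rash and wheezing, both named in 9.4 F, are in 0 of 6. Four rows begin with a pause, and 0 of those 4 name who decides on restart. Two begin with a stop, and 1 of those 2 names a decision-maker.

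**Step 2. Urticaria.** Under 9.4 F any sign of a transfusion reaction means stop, and urticaria is a named example. Under Appendix F the same sign leads to resumption once it has reasonably resolved. The immediate action agrees, because the flow halts under both. What follows does not.

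**Step 3. Hypoxemia.** Ordinary hypoxemia does not trigger the mandatory stop in 9.4 F; only hypoxemia meeting item 4 does, and item 4 requires more than 30 minutes' persistence. Three rows listing hypoxemia say pause and resume with no exception for item 4; the fourth, Infection/Endotoxemia, says stop. While qualifying hypoxemia persists unimproved, the infusion stays halted under both texts. They can differ only on restart after improvement.

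**Step 4. Precedence.** No sentence in Protocol 9.4, Appendix F, Appendix H or SAP Section 5 says which text controls.

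**Step 5. Time available for a restart.** Appendix H 3.3 requires completion within 4 hours (240 minutes) of the start of thaw; Appendix E gives 60-80 minutes for the infusion.

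- 240 − 80 = 160 minutes
- 240 − 60 = 180 minutes

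So 160-180 minutes must cover preparation, transport, checks and any halt together. This does not measure the effect of the conflict; it shows only that restart authority is better settled beforehand.

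**Step 6. Background on frequency.** Protocol 3.6 reports no pre-specified infusion-related events in Phase 2a, which had 40 hMSC patients (Protocol 3.8). The exact two-sided 95% upper limit for 0 of 40 is 1 − 0.025^(1/40) = 0.088, or 8.8%. This covers all pre-specified events with a washed product, whereas DMSO is now left in (Protocol 3.4). It does not estimate urticaria in this trial.

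**The case against.** The strongest reply is that the texts can be read together. Section 9.4 F does not call its stop permanent, and within Appendix F a stop can itself be followed by a restart. On that view 9.4 F governs the halt and Appendix F what comes next. Protocol 3.7.2.2 does speak of terminating the infusion, but for cardiovascular and respiratory criteria, not urticaria. So a reader might infer that any resumption after urticaria breaches 9.4 F; the documents do not support that. What stands is that 9.4 F says nothing on restart while Appendix F directs it, and nothing joins the two.

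A reader might also infer that Appendix F names nobody to decide on restart. That is wrong for the appendix as a whole, since the Transfusion Incompatibility row names the attending BMT physician. It is right for the Hypersensitivity row and the other pause rows.

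Nor does every item 5 event conflict with Appendix F. A picture judged to be incompatibility or transfusion-related infection has a matching row that begins with a stop. The gap is urticaria judged to be hypersensitivity, set against the 9.4 F rule for any sign.

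Finally, Appendix H 3.1 keeps a study physician present throughout, and the Coordinating Center reviews each site's procedure before the trial starts there. Both reduce the risk of divergent practice. Neither provision says which text must be followed, and the study physician is not assigned the restart decision. Site procedures, which are not among the documents, may settle it locally.

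**Conclusion.** The inconsistency is real and should be corrected. For urticaria the body text and the bedside guidance give different instructions, the pause-and-resume row leaves restart unassigned, two other named stop signs are missing from the guidance, and precedence is unstated. The hypoxemia point is secondary: it is confined to restart after improvement of hypoxemia that met item 4.

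Few patients are likely to be affected, though that is a judgement, since no urticaria rate is given. A reader might expect consequences for the analysis. There are none: the modified ITT and Safety populations include everyone who starts the infusion whether or not it is completed, and event reporting does not depend on restart. The conclusion rests on the protocol and SAP wording alone and assumes no site procedure overrides it.

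**What to change.** State in Protocol 9.4 F that it governs. Amend Appendix F and Appendix H 4.11 so that urticaria, rash, wheezing or bronchospasm, or any Section 6.2.2 event, means stop. Allow restart only on the documented decision of the blinded study physician at the bedside, within the existing 4-hour limit. Keep pause-and-resume for signs that meet neither rule, and keep the attending BMT physician's role for suspected incompatibility as written.

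The study physician is the better choice for the added decisions. BMT laboratory staff who prepare product are unblinded (Protocol 8.11) and the BMT team holds the assignments (SAP 12.3). The documents do not state the attending BMT physician's own blinding status.

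If the investigators do intend resumption after isolated urticaria, amend 9.4 F and SAP Section 5 to say so and name the same study physician.

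The cost is wording, carried into site procedures. The downside is a short delay while the physician decides, and an occasional partial dose when the infusion is not restarted.
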